4.6. Study Days and Visit Windows

Study days will be numbered relative to the 1st day of study drug administration. The start of treatment (visit 2 or day 1) is defined as the date on which a patient receives the 1st dose of study drug, as recorded on the study drug diary. The 1st day for the patients rolling over from the pivotal efficacy studies will be the day when they receive the 1st dose of study drug after finishing their procedures/assessments for the pivotal study EOT visit ([Figure 1](#) and [Figure 2](#)). Days will be numbered relative to study start (ie, ..., -2, -1, 1, 2, ...; with day 1 being the start of study drug and day -1 being the day before the start of study drug).

The 4-week (28-day) visit windows for the e-diary based efficacy endpoints will be determined based on the actual dosing day. The run-in phase for the new patients is defined as day -28 to -1 before the 1st injection on day 1. Treatment is from the visit 2 to visit 14 or the EOT visit. Month 1 is from the date/time of the 1st dose of study drug administration on day 1 to the date/time just

before the 2nd dose. Month 2 is from the date/time of the 2nd dose to the date/time just before the 3rd dose. Month 3 is from the date/time of the 3rd dose, and so on.

Throughout this document, all by month efficacy summaries for the headache data will refer to these visit windows.

For all other by-visit summaries, if there are multiple assessments at a postbaseline visit then the last non-missing assessment at that visit will be used for the summary. This includes assessments at the scheduled and unscheduled visits.

Endpoint for analyses and summaries is the last observed postbaseline data. For patients who withdraw from the study, their safety data at the early termination visit will be excluded from the by-visit summaries but will be included in the endpoint summaries.

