- Should the abnormality ($\geq 3\times$ the ULN in case baseline was within the normal range or $\geq 2\times$ the ULN in case the baseline value was above ULN but still $<5\times$ the ULN) persist further, the patient will be followed according to the investigator's discretion, but a blood sample for ALT, AST, GGT, ALP, and total and direct bilirubin should be sent to the central laboratory at least once a month.

ALT or AST $\geq 5\times$ but Less Than $8\times$ the ULN

In addition to the above procedures required for any elevation to levels $>3\times$ the ULN:

- Alanine aminotransferase, AST, GGT, ALP, total and direct bilirubin, CBC and differential count (to assess for eosinophilia), and INR should be monitored twice a week.
- At least for every other measurement, the tests should be sent to the central laboratory. The rest of the tests may be sent to a local laboratory. The INR should always be sent to a local laboratory.

ALT or AST $\geq 8\times$ the ULN

In addition to the above procedures required for any elevation to levels $>3\times$ the ULN:

- The study drug should be discontinued immediately, and the early withdrawal visit should be performed.
- For follow-up guidance, please see below section “Follow-Up of Liver Enzymes After Stopping Rules Are Met.”

Stopping Rules

In the following circumstances, the study drug will be discontinued immediately:

- any increase in ALT or AST to $\geq 3\times$ the ULN, combined with INR $>1.5\times$ the ULN or total bilirubin $>2\times$ the ULN
- any increase in ALT or AST to $\geq 3\times$ the ULN, which is accompanied by symptoms clearly associated with impaired liver function (eg, vomiting, nausea, fever, rash, eosinophilia) and not deemed related to other diseases (eg, vomiting or nausea triggered by migraine)
- any increase in ALT or AST to levels ≥ 5 but $<8\times$ the ULN, which is persistent for ≥ 2 weeks of repeated measurements
- any increase in ALT or AST to levels $\geq 8\times$ the ULN
- in any case where monitoring of liver enzymes cannot be performed according to the protocol guidance

Follow-Up of Liver Enzymes After Stopping Rules Are Met

- A patient who meets the above criteria for discontinuation of the study drug should be invited to the site to return the study drug. Early withdrawal visit activities should be performed as soon as possible.
- Liver enzymes should be monitored until normalization or stabilization of the abnormality, according to the discretion of the investigator.

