- In any case, following the early withdrawal visit, the minimal follow-up period will be 30 days and will include measurement of liver enzymes at least once weekly (may be performed in local laboratory, with at least 1 test being sent to the central laboratory).
- Every effort should be made to complete the additional tests/evaluations, as described above.

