4. GENERAL ISSUES FOR DATA ANALYSIS

4.1. General

Descriptive statistics for continuous variables include count (n), mean, standard deviation (SD), standard error (SE), median, minimum, and maximum. Descriptive statistics for categorical variables include patient counts and percentages.

Summaries of potentially clinically significant abnormal values will include all postbaseline values (including scheduled, unscheduled, and early termination visits).

Endpoint for safety analyses and summaries is the last observed postbaseline data (see Section 4.6 for the definition).

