7.6. Clinical Laboratory Tests

Clinical laboratory tests (serum chemistry, hematology, coagulation, and urinalysis) will be performed at the time points detailed in [Table 1](#) and [Table 2](#) using the central laboratory. Specific laboratory tests to be performed are listed below in [Table 6](#).

Table 6: Clinical Laboratory Test

Serum chemistry	Hematology	Coagulation	Urinalysis

 • calcium • phosphorus • sodium • potassium • chloride • carbon dioxide • magnesium • glucose • blood urea nitrogen • creatinine • ALT • AST • total bilirubin • direct bilirubin • indirect bilirubin (calculated) • lactate dehydrogenase • GGT • ALP • albumin • creatine phosphokinase • total protein 	
 • hemoglobin • hematocrit • RBC count • RBC indices 
 - mean corpuscular volume - mean corpuscular hemoglobin concentration - RBC distribution width • platelet count • WBC count and differential count (absolute values and percentages) 
 - neutrophils - lymphocytes - eosinophils - monocytes - basophils 	
 • prothrombin time • partial thromboplastin time • INR 	
 • color and appearance • specific gravity • pH • blood (hemoglobin) • glucose • albumin • protein • ketones • leukocyte esterase • nitrite • direct bilirubin • microscopic 
 - bacteria - RBCs - WBCs - casts - crystals

Laboratory tests results and changes from baseline for chemistry, hematology, urinalysis, and coagulation laboratory tests will be summarized by visits for each treatment group using descriptive statistics. Shifts (below, within, and above the normal range) from baseline to each visit and endpoint will be summarized using patient counts.

The incidence of potentially clinically significant abnormal results will be summarized using descriptive statistics with the criteria specified in [Table 7](#). The potentially clinically significant abnormal laboratory values will include all postbaseline values (including scheduled, unscheduled, and early termination visits) for the summaries. Listings of patients who have potentially clinically significant abnormal laboratory data will be presented.

Table 7: Criteria for Potentially Clinically Significant Laboratory Values

Test	Criterion value
Serum chemistry	
ALT	$\geq 3 \times \text{ULN}$
AST	$\geq 3 \times \text{ULN}$

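### The laboratory endpoint has no end-of-treatment limit, so a liver-enzyme rise that resolves after withdrawal can vanish from the baseline-to-endpoint shift

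*SAP*

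**What the plan says.** SAP 4.1 states: "Endpoint for safety analyses and summaries is the last observed postbaseline data". SAP 4.6 repeats the rule: "Endpoint for analyses and summaries is the last observed postbaseline data". Neither section limits it to values obtained on treatment or up to the EOT visit. SAP 4.6 then says that, for patients who withdraw, safety data from the early-termination visit stay out of the by-visit summaries but go into the endpoint summaries.

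SAP 7.6 uses this endpoint for laboratory data: "Shifts (below, within, and above the normal range) from baseline to each visit and endpoint will be summarized using patient counts". It plans no shift to the worst post-baseline value. On PCS results it says: "The potentially clinically significant abnormal laboratory values will include all postbaseline values (including scheduled, unscheduled, and early termination visits) for the summaries". It adds: "Listings of patients who have potentially clinically significant abnormal laboratory data will be presented".

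Protocol Appendix E covers patients who meet a liver stopping rule: "Liver enzymes should be monitored until normalization or stabilization of the abnormality, according to the discretion of the investigator". After the early-withdrawal visit, "the minimal follow-up period will be 30 days and will include measurement of liver enzymes at least once weekly". These tests may be done locally, with at least one sent to the central laboratory.

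**The concern.** A last-value rule is harmless when the last value is the end-of-treatment value. For most patients it is, because Protocol Tables 1 and 2 schedule no clinical laboratory tests at the final visit (visit 15). Patients stopped for liver enzymes are different. Appendix E generates later tests for them, off drug and because of the event, and continues until the values settle. If those tests count as last observed data, the endpoint shift records recovery from the event rather than the event.

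This matters for three reasons:
- Changes in laboratory results are among the safety endpoints that Protocol 9.5.1 and 9.7.1 make primary.
- Protocol 1.4.1.1 names liver enzyme elevations as a potential risk.
- The study has no placebo arm and no data monitoring committee (Protocol 3.8.3), and SAP 4.4 plans no inferential analysis, so readers depend on the descriptive tables. SAP 2.5.1 also plans an interim report on these data for the licence application.

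**Working it through.** The plan gives no figure to reproduce. The check applies the rules of SAP 4.6 and 7.6 to assumed ALT courses and reads off each display.

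**Inputs from the documents**
- Endpoint: last observed post-baseline value (SAP 4.1, 4.6).
- By-visit shifts: early-termination visit left out (SAP 4.6).
- PCS criterion for ALT and AST: 3 x ULN or more, any post-baseline value (SAP 7.6, Table 7).
- Follow-up after early withdrawal: at least weekly for at least 30 days (Appendix E). 30 / 7 = 4.3, so at least 4 later tests.
- Scheduled post-dose laboratory visits: 4, 6, 8, 10, 12 and 14 (Protocol Tables 1 and 2).

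**Assumed courses** (ALT in multiples of ULN; illustrative only; ET = early termination on day 124)
- A: baseline 0.8; V4 0.8; V6 8.5; ET 6.0; weekly follow-up 4.0, 2.5, 1.5, 0.9 (days 131 to 152).
- B: baseline 0.8; V4 0.8; V6 0.9; ET 9.0; follow-up as in A.
- C: as A, but no post-withdrawal tests enter the tables.
- D: as A, but follow-up stabilises at 1.4.
- E: as A, but baseline and V4 are 1.4.
- F: baseline 0.8; V4 2.5; V6 0.9; V14 0.9; no withdrawal.

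| Course | By-visit category | Endpoint if last observed | Endpoint if ET value | PCS | Worst value |
|---|---|---|---|---|---|
| A | above at V6 | within | above | yes | above |
| B | within throughout | within | above | yes | above |
| C | above at V6 | above | above | yes | above |
| D | above at V6 | above | above | yes | above |
| E | above at V4 and V6 | within | above | yes | above |
| F | above at V4 | within | not applicable | no | above |

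**Reading the table**
- A and B give the literal result: normal-to-normal in the endpoint row. In B the rise is missing from both shift displays.
- C, D and E show the limits. C and D appear as a shift to above range. E appears as above-to-within, which is not an absence of shift.
- A to E all enter the PCS table and listing. Every enzyme threshold among the Appendix E stopping rules is 3 x ULN or higher, so a stopping-rule value in the database also meets the PCS criterion.
- F concerns smaller rises that resolve. Only one by-visit table shows it; neither the endpoint shift nor the PCS outputs do.
- A worst-value shift gives above range in all six courses, and its result does not depend on which endpoint reading is used.

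**The case against.** The strongest objection is that SAP 4.6 has already settled the matter. Its only specific statement about withdrawn patients puts their early-termination data into the endpoint summaries, and Appendix E wants that visit done as soon as possible after stopping. If that value is the endpoint, A and B show the rise. This is a fair reading, but not the only one. The sentence makes the value eligible and does not exclude later values, while the sentence before it says last observed. Two programmers could produce different tables.

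A second objection is that follow-up tests may never reach these tables. SAP 7.6 describes scheduled tests at the central laboratory, whereas most post-withdrawal tests may be local. This also stands as uncertainty. However, at least one follow-up test must go to the central laboratory, Appendix E has local results entered in the CRF (stated under its guidance for 3 to 5 x ULN), and the PCS rule shows that unscheduled values are expected in the data.

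Two stronger inferences are tempting, and the documents support neither:
- **That the plan hides liver signals, or that only the PCS outputs keep them.** A rise at a scheduled visit normally appears in that visit's shift. SAP 7.3 also summarises and lists events leading to discontinuation and protocol-defined events, which include possible drug-induced liver injury. Protocol 7.1.1 requires liver injury with raised bilirubin or INR to be reported as serious.
- **That every patient stopped for liver enzymes would show no shift.** This needs a normal baseline, normalisation rather than stabilisation, and post-withdrawal values counted as last observed.

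**Conclusion.** The point holds as a gap in one display. On the literal wording, a patient with a normal baseline who recovers after withdrawal is counted as normal-to-normal in the baseline-to-endpoint laboratory shift. If the rise was first seen at the early-termination visit, the by-visit shifts omit it as well.

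The size is limited. One shift display is affected, or two in the early-termination case. The PCS and adverse event outputs are unaffected, and no test or decision rule depends on the endpoint row. The number of patients cannot be derived, because the documents give no rate for liver stopping events in this study. The protocol reports no liver-test changes in Phase 1 (1.3.2.1) and no laboratory safety signal in Phase 2b (1.3.2.2).

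The conclusion assumes that post-withdrawal results are in the analysis data and that last observed is applied as written. It is a cheap improvement, worth making because the display concerns a named potential risk, and because SAP 7.8 already summarises the worst post-baseline finding for ECG.

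**What to change.** - **SAP 4.1 and 4.6:** state that the laboratory endpoint is the last post-baseline value up to and including the EOT or early-withdrawal visit, and that later follow-up tests are excluded from it.
- **SAP 7.6:** add a shift from baseline to the worst post-baseline value for ALT, AST, ALP and total bilirubin, in line with the ECG rule in SAP 7.8.

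The first change removes the ambiguity. The second makes the display insensitive to recovery after withdrawal and also captures rises below 3 x ULN that resolve. Neither touches any clinical rule in Appendix E. The cost is one sentence (in two places) and one extra table; the liver results may look slightly less favourable.

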First treatment administration (ie, for this study) will occur at visit 2, and additional doses will be administered at each visit (approximately every 4 weeks) through visit 13. Patients will return for the EOT visit (visit 14) approximately 4 weeks after administration of the final dose of study drug, and they will return approximately 7.5 months (225 days [the approximate equivalent of 5 half-lives]) after administration of the final dose of the study drug for collection of adverse event and concomitant medication information and samples for pharmacokinetic, immunogenicity, and biomarker analyses.

Headache information will be captured using an electronic headache diary device as follows:

- For patients rolling over from the pivotal efficacy studies, headache information will be captured daily during the first 3 months, during the 4-week period after visit 7, and during the 4-week period after visit 13.

- For patients not rolling over from the pivotal efficacy studies, headache information will be captured daily during the first 4 months, during the 4-week period after visit 7, and during the 4-week period after visit 13.

Assessments of migraine-related disability and change in quality of life (using the HIT-6 or MIDAS questionnaire, PHQ-2/PHQ-9, PGIC scale, MSQOL questionnaire, EQ-5D-5L questionnaire, and WPAI questionnaire), safety evaluations, and collection of pharmacokinetic, immunogenicity, and biomarker samples will be performed throughout the study according to the schedules of assessments ([Table 1](#), [Table 2](#), and [Table 3](#)) and [Section 3.14](#).

[figure not shown]
Patients who withdraw from the study before completing the 12-month treatment period will have EOT visit (visit 14) procedures and assessments performed at their final visit, and they will be asked to return for the follow-up visit approximately 7.5 months (225 days [the approximate equivalent of 5 half-lives]) after their last dose of study drug.

The study schemas for patients with CM and EM who receive study drug in the current study are presented in [Figure 1](#) and [Figure 2](#), respectively.

The end of the study is defined as the date the last patient attends the follow-up visit (visit 15).

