3.14. Study Procedures

Study procedures and assessments with their timing are summarized in [Table 1](#) (patients rolling over from the pivotal efficacy studies), [Table 2](#) (patients not rolling over from the pivotal efficacy studies), and [Table 3](#) (patients rolling over from the pivotal efficacy studies for ADA assessment only). Detailed by-visit information is provided in the sections following the table. Detailed descriptions of each assessment are provided in Section [6](#) (efficacy assessments), Section [7](#) (safety assessments), and Section [8](#) (pharmacokinetic and other assessments).

Table 1: Study Procedures and Assessments for Patients Rolling Over from the Pivotal Efficacy Studies

Study period	Pre-treatment period ^a	Treatment period													Follow-up period
		V1	V2 ^b	V3	V4	V5	V6	V7	V8	V9	V10	V11	V12	V13	
Procedures and assessments (completed before dosing, when applicable, unless otherwise noted)	Screening days -28 to -1	Dose 1 day 0 (±5 days)	Dose 2 day 28 (±5 days)	Dose 3 day 56 (±5 days)	Dose 4 day 84 (±5 days)	Dose 5 day 112 (±5 days)	Dose 6 day 140 (±5 days)	Dose 7 day 168 (±5 days)	Dose 8 day 196 (±5 days)	Dose 9 day 224 (±5 days)	Dose 10 day 252 (±5 days)	Dose 11 day 280 (±5 days)	Dose 12 day 308 (±5 days)	EOT/early withdrawal day 336 (±5 days)	Final visit day 533 (±15 days)
Informed consent		X													
Inclusion and exclusion criteria		X													
Randomization ^c		X													
Full physical examination, including weight		X ^d					X	X					X	X	X
12-lead ECG ^e		X ^d												X	
Vital signs measurement ^e		X ^d	X	X	X	X	X	X	X	X	X	X	X	X	
Clinical laboratory tests ^f		X ^d		X		X		X		X		X		X	
Urine β-HCG test ^g		X ^d	X	X	X	X	X	X	X	X	X	X	X	X	
Adverse events ^h		X ⁱ	X	X	X	X	X	X	X	X	X	X	X	X	X
Concomitant medication inquiry		X ^j	X	X	X	X	X	X	X	X	X	X	X	X	X ^k
eC-SSRS ^l		X ^d	X	X	X	X	X	X	X	X	X	X	X	X	X
Provide electronic headache diary device		X					X						X		
Complete electronic headache diary entries ^m		X	—————X				X	—X					X	—X	
Review electronic headache diary			X	X	X			X						X	
Return electronic headache diary device					X			X						X	

Clinical Study Protocol with Amendment 01

Study period	Pre-treatment period ^a	Treatment period													Follow-up period
		V1	V2 ^b	V3	V4	V5	V6	V7	V8	V9	V10	V11	V12	V13	

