2.3. Sample Size and Power Considerations

There are no statistical considerations for this sample size. A total of 1842 patients (867 patients from Study TV48125-CNS-30049, 675 patients from Study TV48125-30050, and approximately 300 patients who did not participate in the pivotal efficacy studies) are planned for enrollment, and a 30% drop-out rate is anticipated.

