4.4. Multiple Comparisons and Multiplicity

No inferential analysis will be performed in this study.

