6.4.2.3. Six-Item Headache Impact Test

Summary of the HIT-6 total score will be presented for CM patients by their treatment group and visits/months. The summary and 95% confidence interval of the change from baseline will also be presented by visits/months.

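### Questionnaires completed at early-withdrawal visits can enter the visit 14 (month 12) summaries, because SAP 4.6 keeps early-termination data out of by-visit summaries for safety data only

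*SAP*

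**What the plan says.** - **Withdrawal visit.** Protocol 3.1 says that patients who leave before completing treatment "will have EOT visit (visit 14) procedures and assessments performed at their final visit". Protocol 4.4 likewise asks for everything in the early-withdrawal column of the schedule.
- **Schedule.** Tables 1 and 2 have one V14 column for both situations, headed "EOT/early withdrawal day 336 (±5 days". HIT-6 (CM only), MIDAS (EM only), MSQOL, EQ-5D-5L, PHQ-2/PHQ-9, WPAI and PGIC are all ticked in it.
- **Early-termination rule.** SAP 4.6: "For patients who withdraw from the study, their safety data at the early termination visit will be excluded from the by-visit summaries". Those safety data go to the endpoint (last observed) summaries instead.
- **Windows.** SAP 4.6 defines 28-day windows, counted from the actual dosing day, for the diary endpoints. For other by-visit summaries it takes the last non-missing assessment at the visit and sets no limit on study day.
- **Questionnaire tables.** "Summary of the HIT-6 total score will be presented for CM patients by their treatment group and visits/months" (SAP 6.4.2.3). The other questionnaires follow the same by-visit pattern in SAP 6.4.2.4 to 6.4.2.9. Changes in HIT-6, MIDAS, MSQOL, the EQ VAS and PHQ-9 carry 95% confidence intervals. No endpoint row is named for any questionnaire, whereas one is named for laboratory shifts, vital signs and ECG (SAP 7.6 to 7.8).
- **Drop-out.** SAP 2.3 plans 1842 patients, and "a 30% drop-out rate is anticipated".

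**The concern.** Except for PGIC, which has more time points, the questionnaire endpoints are set at visits 8 and 14 and will be read as the 6- and 12-month results. If withdrawal-visit forms enter the visit 14 row, that row mixes values from about day 336 with values from any earlier day, the latter all from patients who left. The visit 8 row has no such admixture, because withdrawal forms belong to the V14 column. The two rows would then be built differently, and the change between them could reflect that difference instead of the course of disability or quality of life.

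MIDAS has a further problem because it looks back 3 months. A new or placebo-rollover EM patient who leaves before about day 84 (3 x 28) would report some days before active treatment, and the answer would appear as month 12.

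**Working it through.** **Step 1. Does any rule keep these values out?**

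| Possible safeguard | Where | Covers questionnaires? |
|---|---|---|
| Early-termination exclusion | SAP 4.6 | No, safety data only |
| Day windows | SAP 4.6 | No, diary only |
| Early discontinuers counted as non-responders | SAP 6.4.1.1 | No, diary responders only |
| FAS membership | SAP 3.3 | No; 10 diary days after the first injection suffice, so a day-40 leaver can qualify |
| Last assessment tied to the 12th dose | SAP 6.1 | PGIC only, as a description without an enforcing rule |

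No stated rule removes HIT-6, MIDAS, MSQOL, EQ-5D-5L, PHQ or WPAI values obtained at withdrawal. The safety sentence also suggests that early-termination data would otherwise reach by-visit summaries.

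**Step 2. The plan's own figure.** SAP 2.3 gives 867 + 675 + 300 = 1842, which reproduces. There is no power calculation to check.

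**Step 3. Expected withdrawals at 30%.** The 300 new patients are split equally between CM and EM, as planned.

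- All: 0.30 x 1842 = 552.6, about 553; remaining 1842 - 552.6 = 1289.4, about 1289.
- CM: 867 + 150 = 1017; 0.30 x 1017 = 305.1, about 305; remaining about 712.
- EM: 675 + 150 = 825; 0.30 x 825 = 247.5, about 248; remaining about 578.

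**Step 4. Share of visit 14 records from withdrawal visits.** Let r be the fraction of withdrawers who complete the forms. The documents give no value, so r is an assumption shown over a range. Every completer is taken to supply a form.

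Share = 552.6r / (552.6r + 1289.4)

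| r | Withdrawal forms | Share of visit 14 records |
|---|---|---|
| 25% | 138 | 9.7% |
| 50% | 276 | 17.6% |
| 75% | 414 | 24.3% |
| 100% | 553 | 30.0% |

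The shares are the same within CM (HIT-6) and EM (MIDAS), since 30% is applied to each.

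**Step 5. Effect on the mean.** Shift = share x (withdrawer mean - completer mean). The documents give no value for that difference. Each 1-point difference moves the visit 14 mean by about 0.10 (r = 25%) to 0.30 points (r = 100%).

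**The case against.** The strongest reply is that the SAP treats early termination as its own kind of visit. Where it wants such data included, as for potentially clinically significant values (SAP 4.1, 7.6, 7.7), it lists scheduled, unscheduled and early-termination visits. The sentence in SAP 4.6 on other by-visit summaries names only scheduled and unscheduled ones. One could conclude that early-termination questionnaires never reach a visit row, and that the safety sentence exists only to route safety data to endpoint summaries. This reading is possible. It does not settle the matter, because the protocol itself calls the withdrawal assessments visit 14 and the SAP then gives those questionnaire values no place at all. Two programmers could produce different tables.

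Several limits stand in full:

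- A reader might infer that the forms *are* stored as visit 14. No document states the database label.
- A reader might take PGIC to be equally exposed. SAP 6.1 places its last assessment 4 weeks after the 12th dose, so it is partly protected.
- A reader might extend the MIDAS look-back problem to all EM patients. Active rollovers were already on the same treatment in the pivotal study, so it does not apply to them.
- A reader might infer that visit 8 excludes patients who withdraw. It does not: those leaving after visit 8 contribute their regular visit 8 values.
- Patients who stop drug but stay in the study are encouraged to attend regular visits (Protocol 3.14.4.1). Diary endpoints are unaffected.

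**Conclusion.** The concern holds as a gap in the rule: as written, early-withdrawal values of HIT-6, MIDAS, MSQOL, EQ-5D-5L, PHQ and WPAI can enter the month-12 summaries. At 30% drop-out, with 25% to 100% of withdrawers completing the forms, about 10% to 30% of visit 14 records would be affected.

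The 30% figure should not be read as the expected share. It is the ceiling, and it requires every withdrawer to complete the forms, including those lost to follow-up. It also refers to the final analysis. For the data cut in SAP 2.5.1 the share depends on a cut-off date that is not given.

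Nor do the documents support a claim about error rates or power. SAP 4.4 states "No inferential analysis will be performed in this study", and all efficacy endpoints are exploratory. The consequence is confined to how the visit 14 means, their 95% confidence intervals and the comparison with visit 8 are read. The direction and size of any shift are unknown. The correction is cheap and worth making before the tables are programmed.

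**What to change.** In SAP 4.6, widen the early-termination exclusion from safety data to safety and questionnaire data, naming HIT-6, MIDAS, MSQOL, EQ-5D-5L, PGIC, PHQ and WPAI. Add an endpoint (last observed) row to each questionnaire table in SAP 6.4.2, so that the early-termination values are still reported.

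The cost is one amended sentence and one row per table, with no new data collection. The drawback is a smaller visit 14 n: at 30% drop-out at most about 1289 overall, about 712 for HIT-6 and about 578 for MIDAS. That row describes only patients still in the study, while visit 8 still includes some who leave later. It should therefore be read beside the endpoint row.
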